3 STUDY METHOD

This is a pragmatic randomized quality improvement pilot trial to assess the feasibility and effectiveness of an adapted Care Ecosystem dementia care training for pre-existing nurse care managers who provide care management to high-risk patients. 15 integrated care management program (iCMP) nurse care managers were randomly assigned to receive early Care Ecosystem training (intervention) and the remaining 15 assigned to received Care Ecosystem delayed training after the study period (control). The time period of interest for outcomes in intervention and control groups is the 6-month period between early and delayed training.

4 STUDY POPULATION AND INCLUSION CRITERIA

The study population consists of all PWD who actively received care management services from the 30 selected nurse care managers at the time of early training.

4.1 Inclusion criteria

Nurse care managers had to meet all of the following inclusion criteria in order to be selected for the study:

- Actively providing care management services within the Mass General Brigham iCMP program

- Ability to understand study procedures and to comply with them for the entire length of the study.

PWD must meet all of the following inclusion criteria in order to be enrolled in the study:

- Medicare beneficiary aligned to the Mass General Brigham Medicare ACO
- ICD-10 diagnosis code consistent with dementia in Medicare claims between August 1, 2019 and July 31, 2020 (excluding diagnoses for diagnostic testing services)
- Actively engaged in iCMP care management services with a nurse care manager enrolled in the study
- Must be at least 18 years old or older

Caregivers must be identified by the iCMP care manager or in the PWD health record as next of kin, health proxy, guardian or primary paid caregiver or by the PCP, must speak English or Spanish, and must be at least 18 years old or older.

4.2 Exclusion criteria

Nurse care managers meeting any of the following criteria will be excluded from the study:

- Fewer than 6 months of employment as an iCMP nurse care manager

PWD meeting any of the following criteria will be excluded from the study:

- Permanent resident of long-term care or deceased at the start of the study

Caregivers of PWD meeting any of the following criteria will be excluded from the study:

- Preferred language other than Spanish or English
- lives out of the country
- unclear relationship with PWD

5 RANDOMIZATION

The study team collaborated with iCMP leadership to identify 30 nurse care managers, prioritizing nurses who served the most disadvantaged practices. The selected nurses were randomly assigned using a randomization process in SAS to either early (intervention group) or delayed training (control group). Persons with dementia and their caregivers who meet inclusion / exclusion criteria were included in the study.

6 SAMPLE SIZE

Preliminary estimates based on 2018 data suggested that on average FTE iCMP nurse care managers in our health system have 10 Medicare beneficiaries diagnosed with dementia on their panels. For this pragmatic quality improvement trial, we planned to engage 30 active iCMP nurse care managers (out of a total of approximately 65 nurse care managers) serving approximately 300 PWD and their caregivers (150 in each arm).

Among the 30 nurse care managers actually selected for the study, a total of 393 PWD met the inclusion criteria, 206 patients corresponding to the 15 intervention nurses and 187 patients corresponding to the 15 control nurses. The population was refined to exclude patients without a designated caregiver, deceased or moved to skilled nursing facility (for full list of exclusions see Figure 1 of cohort flowchart). This validated cohort included 143 PWD in the intervention group, and 113 PWD Controls.

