#### **4 SELECTION AND ENROLLMENT OF PARTICIPANTS**

The study population will consist of all persons with dementia who receive care from 30 selected iCMP nurse care managers. Only nurses who have been completely trained and onboarded into iCMP and with existing patient panels (e.g. 6 or more months of experience) will be asked to participate in the Care Ecosystem Training during this pilot period. The training will be provided as part of on-going QA activities within the program, and similar to other training programs participation by individual nurse care managers will be optional. The study team will work with clinical and operational leaders of the program to reach out to the 30 identified nurse care managers and schedule them for early or delayed training. As the enhanced Care Ecosystem training will provide necessary skills for care managers, it will be implemented as a quality improvement trial.

All PWD who are actively receiving care management services from a selected nurse care manager at the time of early training (end of month 3) will be included in the study. PWD will be identified based on the presence of one or more diagnosis code consistent with dementia during the year ending July 31, 2020. Preliminary estimates based on 2018 claims data suggest that a total of 300 PWD will be included in the study. Caregivers of PWD will be identified using Epic documentation. This study will primarily leverage existing patient data collected within the Epic clinical record and medical claims. These data will be augmented with surveys of PWD caregivers to allow for preliminary evaluations of effectiveness. Both existing data and surveys pose minimal risks to patients. Surveys will include standard language informing caregivers that their decision to participate in the survey will not impact their care or Medicare

benefits, that their participation is voluntary and that the information gathered will only be used to improve care quality for PWD and their caregivers.

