#### **4.1 Inclusion Criteria**

Nurse care managers must meet all of the following inclusion criteria in order to be enrolled in the study:

- Actively providing care management services within the Partners HealthCare iCMP program
- Ability to understand study procedures and to comply with them for the entire length of the study.
- Nurse care managers will be considered subjects for the structured interview component of the pilot, with a waiver of documentation of consent

PWD must meet all of the following inclusion criteria in order to be enrolled in the study:

- Medicare beneficiary aligned to the Partners Medicare ACO
- ICD-10 diagnosis code consistent with dementia in Medicare claims between August 1, 2019 and July 31, 2020 (excluding diagnoses for diagnostic testing services)
- Actively engaged in care management services with a nurse care manager enrolled in the study
- Must be at least 18 years old or older

Caregivers must be identified by the iCMP care manager or in the PWD health record as next of kin, health proxy, guardian or primary paid caregiver or by the PCP, must speak English or Spanish, and must be at least 18 years old or older.

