#### **4.2 Exclusion Criteria**

Nurse care managers meeting any of the following criteria will be excluded from the study:

- Fewer than 6 months of employment as an iCMP nurse care manager

PWD meeting any of the following criteria will be excluded from the study:

- Permanent resident of long-term care or deceased at the start of the study

Caregivers of PWD meeting any of the following criteria will be excluded from the study:

- Preferred language other than Spanish or English

- lives out of the country
- unclear relationship with PWD

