## **6 STUDY PROCEDURES**

There will be five sources of data to be used in these analyses.

- iCMP Program Data: iCMP collects key process measures including patient status within the program, the number of nurse care manager contacts with the patient / caregiver and community resource requests. Nurses can document caregiver strain and PWD behavioral symptoms in structured fields or in iCMP visit notes. Caregiver depression can likewise be assessed and documented in iCMP visit notes. These data will be used to measure iCMP visit frequency and documentation of key patient and caregiver outcomes in order to assess CareEco implementation fidelity. iCMP program data is captured within Epic and flows directly into the Partners data warehouse, where it is co-housed with clinical and financial data from the Partners electronic health record (Epic) and linked claims data for patients in the Medicare MSSP contract.
- Medicare Claims data will be used to identify iCMP patients with dementia at baseline and over time, and to construct measures of health care utilization and costs.
- Epic clinical data will be used to identify patient caregivers, capture PWD and caregiver outcomes documented in the iCMP note, and identify whether medication reconciliation and serious illness conversations / advance care planning occurred related to the iCMP interaction. In addition, Epic contains structured assessments of caregiver strain and PWD behavioral symptoms. All Epic elements flow to tables within the Partners data warehouse.

For some PWD, outcome measures of caregiver strain and PWD behavioral symptoms have already been integrated into Epic documentation (see data sources above). We will compare EMR-integrated measures with measures derived from the surveys of PWD caregivers to determine the relative completeness and quality of the two data sources with a goal of reducing more resource-intensive primary data collection in future studies.

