### **9.3 Outcomes**

The primary outcome for the is pilot is emergency room visits within 6 months. We will rely on Epic and Medicare claims data for all measures of healthcare service utilization and costs, care intensity / quality, documentation of advance care planning, and documentation of medication review. These outcomes will be assessed for all PWD who are cared for by selected nurse care managers using retrospective analysis of existing health care data. We anticipate that this will include 150 PWD among care managers who receive early training and 150 PWD who receive delayed training. These data are housed in an existing data repository; we anticipate minimal missing data. Key secondary outcomes will assess the number of contacts between nurse care managers and care partners, and documented advance care planning; these measures likewise available from the existing data warehouse and we anticipate minimal missing data.

In order to ensure systematic capture of key clinical outcomes within this pilot, we will survey caregivers of PWD receiving care management from the 30 selected nurse care managers and meeting our inclusion and exclusion criteria at months 3 and 9. We expect that a minimum of 50% of caregivers will complete each survey, yielding an expected sample of 75 PWD caregiver respondents completing each survey and 37 PWD caregiver respondents completing both an initial and follow- up survey for nurses assigned to the early and the delayed training. We will assess the completeness and correlation of behavioral symptoms of dementia, caregiver depression, caregiver burden, and PWD quality of life captured via trained nurse care managers (and documented in Epic or iCMP data) with caregiver survey responses.

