7 GENERAL ANALYSIS CONSIDERATIONS

7.1 Analysis populations

7.1.1 Utilization Outcome Cohort

For ED visit outcome measurement, the validated cohort was then further restricted to those with at least 1 member month of Medicare FFS eligibility and alignment to our ACO in the pre and the post period (Intervention n=126, Control n=105), to allow for sufficient utilization data for measurement. (See Figure 1 of cohort flowchart)

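### The ED-visit cohort leaves out people with dementia who have no designated caregiver, a rule that none of the listed patient criteria contains

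*SAP*

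**What the plan says.** Three places define who is to be studied, and all three say everyone.

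- Protocol section 4 includes "All PWD who are actively receiving care management services from a selected nurse care manager at the time of early training" (end of month 3).
- SAP section 4 repeats it: "The study population consists of all PWD who actively received care management services from the 30 selected nurse care managers".
- Protocol 9.3, on the utilization, cost and documentation measures drawn from Epic and claims, says: "These outcomes will be assessed for all PWD who are cared for by selected nurse care managers". The caregiver survey is treated in a separate paragraph.

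The PWD inclusion criteria (Protocol 4.1, SAP 4.1) are ACO alignment, a dementia code in claims, active care management with a study nurse, and adult age. The only PWD exclusion (Protocol 4.2, SAP 4.2) is "Permanent resident of long-term care or deceased at the start of the study". Conditions on how a caregiver is identified, the language spoken, residence abroad and relationship to the PWD are listed as criteria for caregivers.

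SAP section 6 then reports 393 PWD meeting the inclusion criteria (206 early, 187 delayed) and adds: "The population was refined to exclude patients without a designated caregiver, deceased or moved to skilled nursing facility". The result is a validated cohort of 143 early and 113 delayed. For ED visits, SAP 7.1.1 says "the validated cohort was then further restricted to those with at least 1 member month of Medicare FFS eligibility" and ACO alignment in both the pre and post periods, giving 126 and 105.

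**The concern.** A condition that only the caregiver survey needs has been applied to a claims outcome. Protocol section 6 uses Medicare claims "to construct measures of health care utilization and costs", and nothing in that data source depends on a caregiver.

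The primary objective is the feasibility of collecting ED data among the PWD of these practices, and Protocol 9.2 says the pilot is to inform a full-scale study. If PWD without a designated caregiver are removed first, both the ED rate ratio and any feasibility proportion describe a filtered group. A later trial that enrols all PWD under care management could not rely on either figure.

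There is a secondary worry about selection by arm. Nurses are asked to verify each PWD's caregiver (Protocol 6) and are told their training date (Protocol 4.3). The documents do not say which came first, so selection that depends on allocation is possible but not shown.

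**Working it through.** **1. Is the caregiver rule in any PWD criterion?** No. It is not among the four inclusion criteria or the single exclusion, in either document. Protocol 4, Protocol 9.3 and SAP 4 all name the unfiltered population.

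**2. Does the ED analysis need it?** One possible reason is covariate adjustment: Protocol 9.4 adjusts for dementia severity, which the measures table in Protocol 6 takes from the caregiver survey. But the ED model in SAP 8.1 uses baseline utilization, race, ethnicity and age, not dementia severity. With an expected survey response of 50-60% (Protocol 6), having a designated caregiver would not secure that covariate anyway.

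**3. Cohort flow** (counts from SAP 6 and 7.1.1; removals by subtraction):

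| | Early | Delayed | Total |
|---|---|---|---|
| Met inclusion criteria | 206 | 187 | 393 |
| Validated cohort | 143 | 113 | 256 |
| Removed at this step | 63 (30.6%) | 74 (39.6%) | 137 (34.9%) |
| ED cohort | 126 | 105 | 231 |
| Removed by member-month rule | 17 | 8 | 25 |

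The plan's counts add up: 206 + 187 = 393, 143 + 113 = 256, 126 + 105 = 231. The ED cohort is 231/393 = 58.8% of those who met the inclusion criteria.

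**4. Feasibility proportion implied by the SAP cohorts.** The SAP defines none. The natural candidate is 231/256 = 90.2%. The 95% CIs below are Wilson intervals with effective size n / (1 + (m − 1) × ICC), where m is the mean number of PWD per nurse. The ICCs are assumed.

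- Overall (m = 256/30 = 8.53): 85.8-93.4% at ICC 0.01, 85.1-93.7% at 0.05, 84.3-94.1% at 0.10.
- Early, 126/143 = 88.1% (m = 143/15 = 9.53): 80.3-93.1% at ICC 0.05.
- Delayed, 105/113 = 92.9% (m = 113/15 = 7.53): 85.4-96.7% at ICC 0.05.

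**5. What the figure could be over all eligible PWD.** Let r be the number of the 137 who met no listed study-start exclusion. It is unknown, between 0 and 137. With nothing assumed about their claims, the proportion lies between 231/(256 + r) and (231 + r)/(256 + r):

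| r | Eligible | Lower | Upper |
|---|---|---|---|
| 0 | 256 | 90.2% | 90.2% |
| 34 | 290 | 79.7% | 91.4% |
| 69 | 325 | 71.1% | 92.3% |
| 103 | 359 | 64.3% | 93.0% |
| 137 | 393 | 58.8% | 93.6% |

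The lower column assumes none of the r have usable claims, the upper that all do. If 80% of them do (assumed), the figure is (231 + 0.8 × 69)/325 = 88.1% at r = 69 and (231 + 0.8 × 137)/393 = 86.7% at r = 137.

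**6. Difference between arms in the 137.** 39.6% − 30.6% = 9.0 points. With m = 393/30 = 13.1, the p-value is 0.08, 0.14 and 0.21 at assumed ICCs of 0.01, 0.05 and 0.10. The removals mix several reasons, so this is no evidence about the caregiver rule.

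**The case against.** The best defence is that the study is built around dyads. The Protocol précis speaks of measuring PWD and caregivers, Protocol 5.1 personalizes calls to each dyad, and SAP 5 includes PWD and their caregivers who meet the criteria. SAP 6 also states the filter openly, with counts by arm. This makes the restriction understandable, but it does not supply the rule. The précis limits PWD only by dementia indication and active care management, and SAP 5 refers back to criteria that do not mention a caregiver. Protocol 9.3 is explicit that claims outcomes cover all PWD.

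Four points about size do stand.

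- The number lost to the caregiver rule alone cannot be derived. SAP 6 gives three reasons and refers to Figure 1 for the full list. That figure was not available for this review and may give the counts; r could be near zero.
- The SAP defines no feasibility proportion, so 231/256 is only what its cohorts imply.
- The lowest bounds are unlikely. All 393 met criteria requiring ACO alignment and a dementia code in claims, and lacking a caregiver should not make claims unusable. If those removed were as measurable as those kept, the figure would stay at 90.2% for any r.
- SAP 8.1 states no specific hypothesis about ED effect and this is a pilot, so less hangs on the rate ratio than in a confirmatory trial.

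These limit what can be said about the consequence. They do not remove the mismatch between the cohort and the stated population.

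**Conclusion.** The concern holds. The population for the primary outcome departs from Protocol 4, Protocol 9.3 and SAP 4 through a rule in none of the listed PWD criteria, and the ED outcome does not need that rule. Confidence in this textual conflict is high.

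Its numerical effect is not known. At most 137 of 393 PWD are involved, and some of them may fall under the listed exclusion for death or permanent long-term care at study start. The implied feasibility of 90.2% could move in either direction: 71-92% at r = 69, and 59-94% in the extreme case where all 137 were eligible. These ranges assume nothing about the claims of those removed. No bias between arms has been demonstrated. This should be fixed before the ED result or a feasibility figure is used to plan a larger trial.

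**What to change.** 1. In SAP 6 and 7.1.1, define the utilization cohort as all PWD who meet the listed inclusion criteria and none of the listed study-start exclusions, regardless of caregiver status. Apply the caregiver requirement only to the NPI-Q cohort (SAP 7.1.2). Keep the rule of at least one pre and one post member month for the rate ratio only. Handle later death, facility move or loss of alignment through member months.
2. Repeat the baseline-imbalance covariate step of SAP 7.2 in the new cohort, and keep the 231-person cohort as a sensitivity analysis.
3. In SAP 8.1, report the proportion of all eligible PWD with usable pre- and post-period ED claims, overall and by arm, with 95% CIs that allow for clustering by nurse.
4. Reconcile the SAP 6 removal for moving to a skilled nursing facility with the listed exclusion for permanent long-term care at study start, and give removals by reason and arm.

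The cost is SAP wording and a rerun, including covariate selection, on claims already in the repository. There are two downsides. The feasibility figure may rise or fall. PWD without a caregiver may also receive less of a dyad-based intervention and so dilute the ED contrast; comparison with the 231-person analysis would show this.

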7 GENERAL ANALYSIS CONSIDERATIONS

7.1 Analysis populations

7.1.1 Utilization Outcome Cohort

For ED visit outcome measurement, the validated cohort was then further restricted to those with at least 1 member month of Medicare FFS eligibility and alignment to our ACO in the pre and the post period (Intervention n=126, Control n=105), to allow for sufficient utilization data for measurement. (See Figure 1 of cohort flowchart)

7.1.2 Clinical Outcome Cohort

For the NPI-Q Distress outcome measurement, the validated cohort was restricted to baseline and follow-up survey respondents with completed NPI-Q Distress measures (Intervention n=35, Control n=28). (See Figure 1 of cohort flowchart)

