### **9.4 Data Analyses**

Depending on the type of outcome, we will conduct either a linear, negative binomial, or logistic regression, with random effects for nurses, to account for multiple patients nested within the same nurse. The primary predictor will be intervention (iCMP nurse care manager assignment to early CareEco training versus delayed training). Models will be adjusted for a limited number of baseline covariates: dementia stage and severity; Elixhauser score; and patient characteristics. If there are many unbalanced patient or

nurse characteristics, we will use propensity score weighting to adjust for confounding in the face of the limited sample size. Secondary models will examine process measures as potential mediators of the intervention effect on reported outcomes, clinical outcomes, and utilization outcomes. Subgroup analyses will be explored, but given the limited sample size, we do not expect sufficient power to detect effect modification nor significant intervention effects within subgroups.

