2.3 Secondary outcome measure

The secondary outcome is the change in caregiver distress between baseline and 6-month follow-up survey. Caregiver distress is measured by the Neuropsychiatric Inventory Questionnaire (NPI-Q), a brief proxy/caregiver-report of patient severity and caregiver distress across 12 neuropsychiatric symptom domains. Scores on the NPI-Q Distress scale can range from 0 to 60. The NPI-Q has demonstrated reliability and validity in dementia patients.

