7.3 Missing data

Missing data were not imputed for analyses.

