8.2 Secondary outcome analysis

The secondary outcome of change in NPI-Q distress score from baseline survey to 6-month follow-up survey for intervention and control cohorts is compared using a difference-in-differences model with a linear distribution and identity link. Models adjusted for differences in demographic characteristics (race, ethnicity, age) and PHQ-8 at baseline. A point difference of 2 or greater on the NIPQ-Distress scale is generally considered to be clinically meaningful; therefore a difference in differences estimate of 2 or more in this model (i.e., a relative difference of 2 points or more between Intervention and Controls) would suggest a meaningful impact of the Intervention.

We hypothesized a relative decrease in NPI-Q distress in the Intervention group as compared to Controls.

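### The caregiver-distress analysis keeps only caregivers who completed both surveys, discarding single-survey responders and leaving possible selection unassessed

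*SAP*

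**What the plan says.** SAP 2.3 defines the outcome: "The secondary outcome is the change in caregiver distress between baseline and 6-month follow-up survey", measured by NPI-Q Distress. SAP 7.1.2 sets the cohort: "the validated cohort was restricted to baseline and follow-up survey respondents with completed NPI-Q Distress measures", giving "Intervention n=35, Control n=28". The starting point is SAP 6: "This validated cohort included 143 PWD in the intervention group, and 113 PWD Controls". SAP 7.3 adds: "Missing data were not imputed for analyses". Under SAP 8.2 the change "is compared using a difference-in-differences model with a linear distribution and identity link", adjusted for race, ethnicity, age and baseline PHQ-8, and a relative difference of 2 points is treated as meaningful.

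Protocol section 6 invites all caregivers in the eligible cohort at month 3 and at month 9, but says that those who refuse are not contacted again. Protocol 9.3 expects at least 50% response to each survey: 75 respondents per survey in each arm, and "37 PWD caregiver respondents completing both an initial" and a follow-up survey. Protocol 9.4 does not restrict the regressions to completers: "Depending on the type of outcome, we will conduct either a linear, negative binomial, or logistic regression, with random effects for nurses".

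The SAP states no missing-data assumption for the survey outcome, no comparison of completers with other responders and no sensitivity analysis. Its one sensitivity analysis (8.1, removing deaths) is for ED visits.

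**The concern.** A caregiver who answers at month 3 and is then lost contributes nothing, although a baseline distress score is on file. A caregiver reached only at month 9 is also dropped. Two things are at stake.

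The first is precision, in a comparison that is already small.

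The second is selection. The outcome is caregiver distress, which may well influence who answers the second survey. The intervention trains nurses in caregiver support with roughly monthly calls, so the reasons for answering could differ by arm. SAP 7.2 reports that PHQ-8 differed between arms in this cohort. That may be chance, but characteristics are summarised for the analysed cohort only, so a reader cannot see whether the caregivers who were lost looked different.

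This is the SAP's only outcome with a directional hypothesis, and Protocol 9.2 intends the pilot to inform effect sizes for a full-scale study. A selected estimate would carry forward.

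**Working it through.** **1. The protocol's own figures.** With 150 dyads per arm and 50% response per survey: 150 × 0.50 = 75 per survey, and 150 × 0.50 × 0.50 = 37.5 at both (stated: 75 and 37). The plan therefore assumes independent response at the two surveys.

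**2. Are 35 and 28 complete pairs?** The wording of 7.1.2 is slightly loose, so test it on the validated cohort.
- Both surveys: 143 × 0.25 = 35.8 and 113 × 0.25 = 28.3.
- One survey: 143 × 0.50 = 71.5 and 113 × 0.50 = 56.5.

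The reported counts match both-survey response.

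**3. Share analysed.** 35/143 = 24.5%; 28/113 = 24.8%; overall 63/256 = 24.6%. The ED cohort keeps (126 + 105)/256 = 231/256 = 90%.

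**4. Precision lost.** Actual single-survey counts are not visible, so use the protocol's figures per arm: 37 pairs, 75 − 37 = 38 baseline-only, and at most 38 follow-up-only. Assume equal variance at both surveys, within-caregiver correlation r (not given; 0.3 to 0.8 shown) and no clustering by nurse. In units of that variance, the variance of the mean change in one arm is:
- pairs only: 2(1 − r)/37;
- plus baseline-only, by maximum likelihood: (1 − r²)/37 + (1 − r)²/75. Ratio to pairs: [(1 + r) + (1 − r) × 37/75]/2;
- plus 38 follow-up-only as well: 2/[37/(1 − r) + 38]. Ratio to pairs: 37/[37 + 38(1 − r)].

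The SE ratio is the square root:

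| r | + baseline-only | + both groups |
|---|---|---|
| 0.3 | 0.907 | 0.763 |
| 0.5 | 0.934 | 0.813 |
| 0.7 | 0.961 | 0.874 |
| 0.8 | 0.974 | 0.911 |

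The SE falls by 3% to 9% with baseline-only caregivers added, and by 9% to 24% with both groups. With 10 follow-up-only caregivers per arm instead of 38 (an assumption), the cut is 5% to 15%. Applying 50% response to the actual 143 and 113 gives the same ranges.

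**5. When would completers be biased?** Suppose the effect is constant and dropout depends on baseline distress. If the completers' mean baseline in arm k is shifted by s(k), their mean change is shifted by −(1 − r) × s(k). The bias in the difference-in-differences is −(1 − r) × [s(intervention) − s(control)]. It is zero if selection is the same in both arms. A 1-point difference in selection gives a bias of 0.2 points (r = 0.8) to 0.7 points (r = 0.3).

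More generally, let D be the difference in the intervention contrast between completers and all other validated dyads. The bias for the whole validated cohort is (193/256) × D = 0.754 × D: zero if D = 0, 1.5 points if D = 2, and the full 2-point threshold if D = 2.65. The documents give no information on D or on s.

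**6. What the remedy does for power.** Assume SD 6 at each survey, r = 0.5 and two-sided 0.05. The completers' SE is 6 × √[2 × 0.5 × (1/35 + 1/28)] = 1.52, so power for 2 points is about 26%. Multiplying the SE by 0.934 gives about 29%.

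**The case against.** The strongest reply is that no harm has been shown. A reader might infer that complete pairs are biased whenever dropout is related to distress. Step 5 shows otherwise: dependence on baseline distress that is equal in both arms cancels in a difference-in-differences. The completer shares are almost identical, and the model adjusts for baseline PHQ-8. This stands as a reason not to assert bias. It does not close the matter, because equal numbers can be different kinds of caregivers, and PHQ-8 adjustment among completers does not restore the baseline distress of those who left.

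A reader might also infer from 63 of 256 that the cohort rule throws away three quarters of the data. It does not. Most of that gap is survey non-response, Protocol 9.3 openly expected about 25% at both surveys, and no model recovers dyads that never answered.

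Nor is 9% to 24% the expected gain. Refusers are not contacted again, so independent response probably overstates the follow-up-only group, and those caregivers lack the baseline PHQ-8 that SAP 8.2 adjusts for. They also enter after randomisation and training, which could bring in selection of its own.

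Finally, the single-survey counts may appear in the cohort flowchart, which is not visible here. That would settle the numbers but not the analysis rule.

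**Conclusion.** The point holds in limited form. The SAP confines its only secondary outcome to both-survey completers, discards scores already collected, and plans nothing to show whether completers differ from other responders. For the PHQ-8-adjusted model the avoidable loss is modest, about 3% to 9% of the standard error; 9% to 24% is an upper scenario for an analysis without PHQ-8. Both ranges rest on 50% response per survey, correlations of 0.3 to 0.8, equal variances and no clustering by nurse.

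Selection bias is a risk, not a finding. It requires response to depend on distress differently by arm, or the effect to differ between completers and the rest, and the documents neither show nor exclude this. The case for change is that the better analysis is cheap and makes the risk visible.

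**What to change.** - **Main analysis.** Use all validated dyads with baseline NPI-Q Distress, whether or not follow-up was completed. Fit a linear mixed model by maximum likelihood with arm, time, arm × time, caregiver-level correlation, the nurse random effect of Protocol 9.4, and the SAP covariates including baseline PHQ-8.
- **Second version.** Omit PHQ-8 and add follow-up-only responders.
- **Sensitivity analyses.** Keep the 35 and 28 pairs, and add a simple missing-not-at-random analysis, for example shifting the unobserved follow-up scores by a range of values separately in each arm.
- **Reporting.** Tabulate baseline NPI-Q Distress and PHQ-8 for completers against baseline-only caregivers, by arm. State the single-survey counts. Report deaths of persons with dementia separately, because follow-up distress is then undefined rather than missing.

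The cost is SAP wording, a few extra models and one table, on survey data already held in REDCap. The main model relies on missing at random, which is why the last sensitivity analysis is needed. None of this repairs the low power that comes from survey non-response.
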